### **8.3.2 Direct access to source data and documents**

The investigator /institution will allow site trial-related monitoring, audits, IRB / IEC review and regulatory inspections. Direct access must be provided to the CRF and all source documents/data, including progress notes, copies of laboratory and medical test results, which must be available at all times for review by the CRA, auditor and regulatory inspector (e.g. FDA). They may review all CRFs and informed consents. The accuracy of the data will be verified by direct comparison with the source documents described in [section 8.3.1](#). The sponsor will also monitor compliance with the protocol and GCP.

### **8.3.3 Storage period of records**

#### **Trial site(s):**

The trial site(s) must retain the source and essential documents (including ISF) according to contract or the local requirements valid at the time of the end of the trial (whatever is longer).

#### **Sponsor:**

The sponsor must retain the essential documents according to the sponsor's SOPs.

## 8.4 EXPEDITED REPORTING OF ADVERSE EVENTS

BI is responsible to fulfil their legal and regulatory reporting obligation in accordance with regulatory requirements.

Exemptions from expedited reporting are described in [section 5.2.6.2.4](#), if applicable.

## 8.5 STATEMENT OF CONFIDENTIALITY AND PATIENT PRIVACY

Data protection and data security measures are implemented for the collection, storage and processing of patient data in accordance with the principles 7 and 12 of the WHO GCP handbook.

Individual patient data obtained as a result of this trial is considered confidential and disclosure to third parties is prohibited with the following exceptions:

Personalised treatment data may be given to the patient's personal physician or to other appropriate medical personnel responsible for the patient's welfare. Data generated at the site as a result of the trial need to be available for inspection on request by the participating physicians, the sponsor's representatives, by the IRB / IEC and the regulatory authorities.

### 8.5.1 Collection, storage and future use of biological samples and corresponding data

Measures are in place to comply with the applicable rules for the collection and future use of biological samples and clinical data, in particular

- Sample and data usage has to be in accordance with the informed consent
- The BI-internal facilities storing biological samples from clinical trial participants as well as the external banking facility are qualified for the storage of biological samples collected in clinical trials
- An appropriate sample and data management system, incl. audit trail for clinical data and samples to identify and destroy such samples according to ICF is in place
- A fit for the purpose documentation (biomarker proposal, analysis plan and report) ensures compliant usage
- A fit for purpose approach will be used for assay/equipment validation depending on the intended use of the biomarker data
- Samples and/or data may be transferred to third parties and other countries as specified in the ICF

## 8.6 TRIAL MILESTONES

The **start of the trial** is defined as the date when the first patient in the whole trial signs informed consent.

The **end of the trial** is defined as the date of the last visit of the last patient in the whole trial ("Last Patient Completed").

The "**Last Patient Last Treatment**" (LPLT) date is defined as the date on which the last patient in the whole trial is administered the last dose of trial treatment (as scheduled per protocol or prematurely). Individual investigators will be notified of SUSARs occurring with

Proprietary confidential information © 2020 Boehringer Ingelheim International GmbH or one or more of its affiliated companies

the trial medication until 30 days after LPLT at their site. **Early termination of the trial** is defined as the premature termination of the trial due to any reason before the end of the trial as specified in this protocol.

**Temporary halt of the trial** is defined as any unplanned interruption of the trial by the sponsor with the intention to resume it.

**Suspension of the trial** is defined as an interruption of the trial based on a Health Authority request.

## 8.7 ADMINISTRATIVE STRUCTURE OF THE TRIAL

The trial is sponsored by Boehringer Ingelheim (BI).

A Coordinating Investigator is responsible to coordinate investigators at the different sites participating in this trial. Tasks and responsibilities are defined in a contract.

A SMC composed of participating investigators and members of the BI trial team will be established to review individual and aggregated safety and efficacy data to determine the safety profile and risk/benefit ratio and recommend next dose level/does escalation/de-escalation/modification/next cohort size, and appropriateness of further enrolment. Details of the SMC responsibilities and procedures are described in the SMC charter. Regarding SMC please see also [sections 2.1, 3.1, 3.2, 4.1](#) and [7.1](#) of the clinical trial protocol.

Relevant documentation on the participating (Principal) Investigators (e.g. their curricula vitae) will be filed in the ISF.

The investigators will have access to the BI web portal Clinergize to access documents provided by the sponsor.

BI has appointed a Clinical Trial Leader (CT Leader), responsible for coordinating all required activities, in order to

- manage the trial in accordance with applicable regulations and internal SOPs,
- direct the clinical trial team in the preparation, conduct, and reporting of the trial,
- ensure appropriate training and information of Clinical Trial Managers (CT Managers), Clinical Research Associates (CRAs), and investigators of participating countries.

The organisation of the trial in the participating countries will be performed by the respective local or regional BI-organisation (Operating Unit, OPU) in accordance with applicable regulations and BI SOPs, or by a CRO with which the responsibilities and tasks will have been agreed and a written contract filed before initiation of the clinical trial.

Data Management and Statistical Evaluation will be done by BI according to BI SOPs.

Tasks and functions assigned in order to organise, manage, and evaluate the trial are defined according to BI SOPs. A list of responsible persons and relevant local information can be found in the ISF.

A central logistic laboratory service and an IRT vendor will be used in this trial. Details will be provided in the IRT Manual and Central Laboratory Manual, available in the ISF.

## 10. APPENDICES

### 10.1 TIME SCHEDULE FOR PHARMACOKINETIC (PK) SAMPLING

Table 10.1: 1 Time schedule for PK blood [REDACTED] sampling and ECG

Cycle	Visit	Day	Time Point [hh:min]	CRF Time /PTM	Event		
					Drug administr.	PK Blood and ECG	[REDACTED]
1	1	1	Just before drug administration	-0:05		X	[REDACTED]
			0:00	0:00	X		[REDACTED]
			0:30	0:30		X	[REDACTED]
			0:45	0:45		X	[REDACTED]
			1:00	1:00		X	[REDACTED]
			1:30	1:30		X	[REDACTED]
			2:00	2:00		X	[REDACTED]
			2:30	2:30		X	[REDACTED]
			3:00	3:00		X	[REDACTED]
			4:00	4:00		X	[REDACTED]
			6:00	6:00		X	[REDACTED]
			8:00	8:00		X	[REDACTED]
			10:00	10:00		X	[REDACTED]
			12:00	12:00		X a	[REDACTED]
2	2		Just before drug administration	23:55		X	[REDACTED]
4	8		Just before drug administration	167:55		X	[REDACTED]
5	15	15	Just before drug administration	335:55		X	[REDACTED]
			0:00	336:00	X		[REDACTED]
			0:30	336:30		X	[REDACTED]
			0:45	336:45		X	[REDACTED]
			1:00	337:00		X	[REDACTED]
			1:30	337:30		X	[REDACTED]
			2:00	338:00		X	[REDACTED]
			2:30	338:30		X	[REDACTED]
			3:00	339:00		X	[REDACTED]
			4:00	340:00		X	[REDACTED]
							[REDACTED]
			6:00	342:00		X	[REDACTED]
			8:00	344:00		X	[REDACTED]
			10:00	346:00		X	[REDACTED]
			12:00	348:00		X a	[REDACTED]

Table 10.1: 1 Time schedule for PK blood [REDACTED] sampling and ECG (cont.)

Cycle	Visit	Day	Time Point [hh:min]	CRF Time /PTM	Event		
					Drug administr.	PK Blood and ECG	[REDACTED]
	6	16	Just before drug administration	359:55		X	[REDACTED]
	7	22	Just before drug administration	503:55		X	
2	1	1	Just before drug administration	-0:05		X	
3	1	1	Just before drug administration	-0:05		X	
4	1	1	Just before drug administration	-0:05		X	

a) An optional 12-hour postdose PK blood sample should be collected if the patient is willing.

b) [REDACTED]

## 10.2 STATISTICAL APPENDIX INCLUDING MODEL PERFORMANCE AND DATA SCENARIOS

A Bayesian logistic regression model with overdose control will be used to guide dose escalation in this trial. The BLRM is introduced in [Section 7.1](#), which also specifies the prior for the model. After patients in each cohort have completed at least one cycle of treatment, the prior distribution will be updated through Gibbs sampling procedures with the accumulated DLT data from the MTD evaluation period. Posterior probabilities for the rate of DLTs will be summarised from BLRM. Selection of the next dose will be based on these probabilities as well as on other safety and laboratory data.

The purpose of this statistical appendix is to present performance metrics (operating characteristics) that illustrate the precision of the design in estimating the MTD under various dose-toxicity relationships through computer simulation. These results are summarized in [Table 10.2:3](#). In addition, recommendations of the next dose level by the BLRM with overdose control principle are also provided under various hypothetical outcome scenarios in early cohorts to show how it facilitates on-trial dose-escalation decisions (see [Table 10.2:1](#)). For simplicity reasons, a cohort size of 3 patients who are all evaluable is assumed.

### Hypothetical data scenarios

Hypothetical data scenarios are shown in Table 10.2:1. These scenarios reflect potential on-study data constellations and related escalation as allowed by the model. It is assumed that each cohort has exactly three patients who are all evaluable. For each scenario, the probability of overdose for the current dose, as well as the next potential dose and related probabilities of under-dosing, target dose, and over-dosing are shown.

For example, scenario 1 represents the case that no DLT is observed in the first three patients at the starting dose of 4 mg. In this case, the next optimal dose, i.e. the dose with the highest probability of being in the target interval, is 7 mg. Since the escalation is restricted to a maximum of 50 % from the previous dose per protocol, the next dose to be tested in the trial would be 6 mg.

Scenario 4 is the case that one DLT is observed in the first three patient at the starting dose of 4mg and no DLT is observed in second three patient at 4mg; in this case the model recommend to escalate 6 mg . Scenario 5 is the case that one DLT is observed in the first three patient at the starting dose of 4 mg and one DLT is observed in second three patient at 4 mg; in this case the model recommend to 4 mg. Scenario 6 represents the case that 3 patients have been treated at 4 mg and 3 patients at 6 mg, none of them with a DLT. In this case, the model recommends to escalate to 8 mg.

Scenarios 16 to 22 are the cases where doses of 4 mg and 6 mg have been completed with no DLT and the BLRM recommends 8mg to be tested next. More specifically, scenarios 18, 21 and 22 are the cases that dose of 8 mg have been completed and BLRM recommend to reduce to 7mg. Scenario 19, 20 illustrate a case where escalation has proceeded up to the highest dose of 8 mg, where the MTD could be declared at 8 mg.

Scenarios 23 to 26 are the cases that 1 DLT out of 6 patients in 4mg cohort and no DLT in 3 patients in 6 mg cohort, BLRM recommends 7 mg to be tested next. In scenarios 23, the next optimal dose, i.e. the dose with the highest probability of being in the target interval, is 8 mg. In such cases, SMC will suggest whether to open up 8mg cohort or keep treating patients at 7mg. In scenarios 25, the next optimal dose, i.e. the dose with the highest probability of being in the target interval, is 8 mg. In such cases, SMC will suggest whether to open up 8 mg

Proprietary confidential information © 2020 Boehringer Ingelheim International GmbH or one or more of its affiliated companies

cohort or claiming 7 mg as MTD according to BLRM. Scenario 26 illustrates a case when we can claim 7 mg as MTD according to BLRM.

Scenarios 27, 28, 30 and 31 are the cases that no DLT out of 3 patients in 4mg cohort and one DLT in 6 patients in 6 mg cohort, BLRM recommends 7 mg to be tested next. In scenarios 27 and 29, the next optimal dose, i.e. the dose with the highest probability of being in the target interval, is 8 mg. In scenarios 28, the next optimal dose, i.e. the dose with the highest probability of being in the target interval, is 7 mg. Scenario 30 illustrates a case when we can claim 7 mg as MTD according to BLRM. Scenario 31 illustrates a case when we can claim 6 mg as MTD according to BLRM.

Scenarios 32 to 36 are the cases that 1 DLT out of 6 patients in 4mg cohort, no DLT in 3 patients in 6 mg cohort and no DLT in 3 patients in 7 mg cohort BLRM recommends 8 mg to be tested next.

Scenarios 37 to 41 are the cases that 1 DLT out of 6 patients in 4mg cohort, no DLT in 3 patients in 6 mg cohort and one DLT in 6 patients in 7 mg cohort BLRM recommends 8 mg to be tested next.

Scenarios 42 to 46 are the cases that no DLT out of 3 patients in 4mg cohort, one DLT in 6 patients in 6 mg cohort and no DLT in 3 patients in 7 mg cohort BLRM recommends 8 mg to be tested next.

Table 10.2:1 Hypothetical data scenarios

Scenario	Dose (mg)	# Patients	# DLT	Current Dose : P (OD)	Next recommended dose *	Next dose:		
						P (UD)	P (TD)	P (OD)
1	4 mg	3	0	0.026	6 mg [7 mg]	0.636 [0.486]	0.270 [0.339]	0.095 [0.175]
2	4 mg	3	1	0.194	4 mg	0.442	0.365	0.194
3	4 mg	3	2	0.569	NA			
4	4 mg	6	1	0.065	6 mg	0.309	0.459	0.233
5	4 mg	6	2	0.249	4 mg	0.273	0.478	0.249
6	4 mg	3	0					
	6 mg	3	0	0.027	8 mg	0.440	0.375	0.185
7	4 mg	3	0					
	6 mg	3	1	0.153	6 mg	0.427	0.420	0.153
8	4 mg	3	0					
	6 mg	6	1	0.049	7 mg	0.377	0.480	0.143
9	4 mg	3	0			0.304	0.518	0.178
	6 mg	6	2	0.178	6 mg			

Table 10.2:1 Hypothetical data scenarios (cont.)

10	4 mg 6 mg	3 6	0 3	0.397	4 mg	0.484	0.400	0.116
11	4 mg 6 mg	3 6	0 4	0.658	4 mg	0.318	0.449	0.233
12	4 mg 6 mg	6 3	1 0	0.096	7 mg	0.335	0.474	0.192
13	4 mg 6 mg	6 3	1 1	0.243	6 mg	0.215	0.542	0.243
14	4 mg 6 mg	6 6	1 1	0.125	7 mg	0.212	0.553	0.235
15	4 mg 6 mg	6 6	1 2	0.288	4 mg	0.504	0.424	0.072
16	4 mg 6 mg 8 mg	3 3 3	0 0 0	0.058	8 mg	0.604	0.338	0.058
17	4 mg 6 mg 8 mg	3 3 3	0 0 1	0.234	8 mg	0.281	0.485	0.234
18	4 mg 6 mg 8 mg	3 3 3	0 0 2	0.500	7 mg	0.304	0.481	0.214
19	4 mg 6 mg 8 mg	3 3 6	0 0 0	0.023	8 mg	0.731	0.245	0.023
20	4 mg 6 mg 8 mg	3 3 6	0 0 1	0.106	8 mg	0.443	0.451	0.106
21	4 mg 6 mg 8 mg	3 3 6	0 0 2	0.274	7 mg	0.453	0.464	0.083
22	4 mg 6 mg 8 mg	3 3 6	0 0 3	0.501	7 mg	0.287	0.519	0.195

Table 10.2:1 Hypothetical data scenarios (cont.)

23	4 mg	6	1	0.076	8 mg [7 mg]	0.364 [0.483]	0.484 [0.442]	0.152 [0.076]
24	4 mg	6	1	0.209	7 mg	0.234	0.557	0.209
25	4 mg	6	1	0.092	8 mg [7 mg]	0.247 [0.368]	0.560 [0.540]	0.193 [0.092]
26	4 mg	6	1	0.225	7 mg	0.174	0.602	0.225
27	4 mg	3	0	0.052	8mg [7 mg]	0.335 [0.534]	0.492 [0.413]	0.173 [0.052]
28	4 mg	3	0	0.177	7 mg	0.278	0.546	0.177
29	4 mg	3	0	0.224	8 mg [7 mg]	0.222 [0.404]	0.554 [0.530]	0.224 [0.066]
30	4 mg	3	0	0.199	7 mg	0.200	0.602	0.199
31	4 mg	3	0	0.363	6 mg	0.263	0.589	0.148
32	4 mg	6	1	0.065	8 mg	0.510	0.425	0.065
33	4 mg	6	1	0.178	8 mg	0.258	0.563	0.178
	6 mg	3	0					
	7 mg	3	0					
	8 mg	3	1					

Proprietary confidential information © 2020 Boehringer Ingelheim International GmbH or one or more of its affiliated companies

Table 10.2:1 Hypothetical data scenarios (cont.)

34	4 mg	6	1	0.023	8 mg	0.637	0.340	0.023
	6 mg	3	0					
	7 mg	3	0					
	8 mg	6	0					
35	4 mg	6	1	0.077	8 mg	0.380	0.544	0.077
	6 mg	3	0					
	7 mg	3	0					
	8 mg	6	1					
36	4 mg	6	1	0.207	8 mg	0.188	0.605	0.207
	6 mg	3	0					
	7 mg	3	0					
	8 mg	6	2					
37	4 mg	6	1	0.100	8 mg	0.366	0.534	0.100
	6 mg	3	0					
	7 mg	6	1					
	8 mg	3	0					
38	4 mg	6	1	0.226	8 mg	0.177	0.597	0.226
	6 mg	3	0					
	7 mg	6	1					
	8 mg	3	1					
39	4 mg	6	1	0.041	8 mg	0.490	0.468	0.041
	6 mg	3	0					
	7 mg	6	1					
	8 mg	6	0					
40	4 mg	6	1	0.109	8 mg	0.272	0.619	0.109
	6 mg	3	0					
	7 mg	6	1					
	8 mg	6	1					
41	4 mg	6	1	0.236	8 mg	0.139	0.625	0.236
	6 mg	3	0					
	7 mg	6	1					
	8 mg	6	2					
42	4 mg	3	0	0.074	8 mg	0.495	0.431	0.074
	6 mg	6	1					
	7 mg	3	0					
	8 mg	3	0					

Table 10.2:1 Hypothetical data scenarios (cont.)

43	4 mg	3	0	0.200	8 mg	0.240	0.560	0.200
	6 mg	6	1					
	7 mg	3	0					
	8 mg	3	1					
44	4 mg	3	0	0.025	8 mg	0.615	0.360	0.025
	6 mg	6	1					
	7 mg	3	0					
	8 mg	6	0					
45	4 mg	3	0	0.082	8 mg	0.369	0.549	0.082
	6 mg	6	1					
	7 mg	3	0					
	8 mg	6	1					
46	4 mg	3	0	0.232	8 mg	0.162	0.606	0.232
	6 mg	6	1					
	7 mg	3	0					
	8 mg	6	2					

\* Model recommendation is higher than allowed by additional rules in the CTP. Dose in brackets represents next dose with taking into account the CTP-specific rules.

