## 2. TRIAL OBJECTIVES AND ENDPOINTS

### 2.1 MAIN OBJECTIVES, PRIMARY AND SECONDARY ENDPOINTS

#### 2.1.1 Main objectives

The primary objective of this trial is to confirm the safety and tolerability of previously identified MTD, BI 3011441 8mg (in Caucasian FIH study) as a single agent when administered orally to adult Japanese patients with NRAS/KRAS mutation positive advanced or metastatic refractory solid tumours.

The MTD will be determined based on the frequency of patients experiencing DLTs during the MTD evaluation period. The MTD evaluation period is defined as first treatment cycle (28 days). At the end of the dose escalation, the BLRM will be rerun using all DLTs. This result as well as all available data will be used to define the recommended dose (RD).

The secondary objectives is to evaluate the safety and tolerability, and characterise PK of BI 3011441 as monotherapy in Japanese patients with NRAS/KRAS mutation positive advanced solid tumours

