#### 2.1.2 Primary endpoint(s)

- MTD defined as the highest dose with less than 25% risk of the true DLT rate being equal or above 33% during the MTD evaluation period. For the definition of DLTs, refer to [Section 5.2.6.3](#)
- Number of patients with DLTs in the MTD evaluation period.

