The Safety Monitoring Committee (SMC, see [Section 8.7](#)) will recommend the size for the next dose escalation cohort. After all patients in a cohort have either experienced a DLT or have been observed for at least the MTD evaluation period without experiencing a DLT, the Bayesian model will be updated with the newly accumulated data. The overdose risk will then be calculated for each dose, and escalation will be permitted to all doses which fulfil the EWOC criterion and the additional 50 % escalation rule. Based on the model and on

Proprietary confidential information © 2020 Boehringer Ingelheim International GmbH or one or more of its affiliated companies

additional information (PK, PD, patient profiles), the members of the SMC will reach a joint decision on the next dose level to be investigated.

If DLTs are observed in the first two consecutive patients of a previously untested dose level, subsequent enrolment to that cohort will be stopped. The BLRM will be re-run to confirm that the dose level still fulfils the EWOC principle. Based on this information, the SMC will evaluate whether the next patients will be enrolled at the same dose level, or if they will be enrolled at a lower dose level.

The SMC may recommend stopping the dose escalation phase after the criterion for MTD ([Section 7.1](#)) is fulfilled. Further patients may be included to confirm this MTD estimate, i.e. to confirm that the EWOC criterion is still fulfilled. If no DLT is observed at a dose of which the efficacy is considered sufficient, the SMC may decide to include an additional number of patients at the same dose level and to declare this dose as the recommended.

The SMC can declare any dose fulfilling the EWOC criterion as the RD, independent of the MTD estimate.

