## 7. STATISTICAL METHODS AND DETERMINATION OF SAMPLE SIZE

### 7.1 STATISTICAL DESIGN – MODEL

The trial will be performed as an open-label trial. The objective of the design is to determine the MTD defined as the highest dose with less than 25% risk of the true DLT rate being equal or above 0.33 (EWOC criterion). The phase I dose-finding will be guided by a Bayesian 2-parameter logistic regression model with overdose control ([R13-4806](#); [R13-4803](#)).

The model is given as follows:

$$\text{logit}(\pi_d) = \log(\alpha) + \beta * \log(d/d^*),$$

where  $\text{logit}(\pi) = \log(\pi/(1-\pi))$ .

$\pi_d$  represents the probability of having a DLT in the MTD evaluation period at dose  $d$ ,  $d^* = 8$  mg is the reference dose, allowing for the interpretation of  $\alpha$  as the odds of a DLT at dose  $d^*$ , and  $\theta = (\log(\alpha), \log(\beta))$  with  $\alpha, \beta > 0$  is the parameter vector of the model. The estimated probability of a DLT at each dose level from the model will be summarized using the following intervals:

Under toxicity: [0.00, 0.16)

Targeted toxicity: [0.16, 0.33)

Over toxicity: [0.33, 1.00]

The BLRM-recommended dose for the next cohort is the level with the highest posterior probability of the DLT rate falling in the target interval [0.16, 0.33) among the doses fulfilling EWOC. Applying the EWOC criterion, it should be unlikely (<25% posterior probability) that the DLT rate at that dose will exceed 0.33. However, the maximum allowable dose increment for the subsequent cohort will be no more than 50 % for each dose level.

The MTD may be considered reached if one of the following criteria is fulfilled:

1. The posterior probability of the true DLT rate in the target interval [0.16 – 0.33) of the MTD is above 0.5, OR
2. At least 12 patients have been treated in the dose escalation phase of the trial, of which at least 6 at the MTD.

The SMC may recommend stopping the dose escalation phase after the criterion for MTD is fulfilled. Further patients may be included to confirm this MTD estimate. If no DLT is observed at a dose of which the efficacy is considered sufficient, the SMC may decide to include an additional number of patients at this dose level and to declare this dose as the dose recommended for further testing

Since a Bayesian approach is applied, a prior distribution  $f(\theta)$  for the unknown parameter vector  $\theta$  needs to be specified.

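### Scenario 25 of Appendix 10.2 lets 7 mg be claimed as MTD although 8 mg still fulfils EWOC, which conflicts with the definition of the primary endpoint

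*Protocol*

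**What the plan says.** Protocol 2.1.2 gives the primary endpoint as "MTD defined as the highest dose with less than 25% risk of the true DLT rate being equal or above 33" per cent, within the MTD evaluation period. Protocol 7.1 and SAP 5.1 repeat the definition. The objective in 2.1.1 concerns one dose: "The primary objective of this trial is to confirm the safety and tolerability of previously identified MTD, BI 3011441 8mg".

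Protocol 7.1 sets the overdose rule, that "it should be unlikely (<25% posterior probability) that the DLT rate at that dose will exceed 0.33". It defines the recommended next dose as "the level with the highest posterior probability of the DLT rate falling in the target interval [0.16, 0.33) among the doses fulfilling EWOC" and caps each increment at 50%. It then says the MTD may be considered reached on either of two criteria:

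- "The posterior probability of the true DLT rate in the target interval [0.16 – 0.33) of the MTD is above 0.5"
- "At least 12 patients have been treated in the dose escalation phase of the trial, of which at least 6 at the MTD"

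For scenario 25, Appendix 10.2 names 8 mg as the next optimal dose and then leaves the SMC to decide between opening an 8 mg "cohort or claiming 7 mg as MTD according to BLRM".

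Protocol 3.1 provides a separate label for a dose chosen on other grounds: "The SMC can declare any dose fulfilling the EWOC criterion as the RD, independent of the MTD estimate".

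**The concern.** A definition built on the highest qualifying dose needs two things: the declared dose passes the overdose rule, and no higher planned dose does. The scenario 25 text offers 7 mg as MTD when the second part is not met, and attributes that claim to the model.

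The trial exists to learn whether 8 mg is tolerable in Japanese patients. If 7 mg were reported as MTD on such data, a reader who applies the definition would conclude that 8 mg had failed the overdose rule. In fact 8 mg would have passed it on the available data without any patient having been treated there.

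**Working it through.** **Inputs.** MTD definition and EWOC limit: P(DLT rate ≥ 0.33) < 0.25 (2.1.2, 7.1). Increment cap: 50% (7.1). Step from 7 to 8 mg: 14.3% (Table 4.1.2:1). Posterior probabilities: Table 10.2:1. Prior: Table 7.1:2.

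**Step 1. Printed figures for scenario 25.**

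| Dose | P(under) | P(target) | P(overdose) | Below 0.25? |
|---|---|---|---|---|
| 7 mg | 0.368 | 0.540 | 0.092 | yes |
| 8 mg | 0.247 | 0.560 | 0.193 | yes |

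- Highest dose fulfilling EWOC: 8 mg, with a margin of 0.25 − 0.193 = 0.057.
- Recommended dose under 7.1: also 8 mg, by 0.560 − 0.540 = 0.020 in target probability.
- Increment: (8 − 7)/7 = 14.3%, within 50%. The table footnote says brackets mark recommendations above what protocol rules allow, but no stated rule blocks 8 mg here.

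**Step 2. Reproducing the figures.** The model is logit(π_d) = log α + β·log(d/8), with the three-component mixture prior and a binomial likelihood, integrated on a grid. Prior overdose probabilities at 4, 6, 7 and 8 mg come out at 0.129, 0.232, 0.310 and 0.421, against 0.128, 0.233, 0.310 and 0.422 in Table 7.1:3. The scenario 25 data are 1/6 at 4 mg and 0/3 at 6 mg. The 7 mg data are not legible in the text available to me, so I assume 1/6. The re-fit then gives an overdose probability of 0.098 at 7 mg and, depending on grid spacing, 0.193 to 0.209 at 8 mg. This agrees with the table, and 8 mg stays below 0.25 throughout.

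**Step 3. The 7.1 criteria in scenario 25.**

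- Applied to 7 mg: criterion 1 is met (0.540 > 0.5). Criterion 2 is met on the assumed data (6 + 3 + 6 = 15 patients, 6 of them at 7 mg).
- Applied to the MTD as defined, 8 mg: criterion 1 is met (0.560 > 0.5) with no patient at 8 mg. Criterion 2 is not met.

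So criterion 1 alone does not require 8 mg to have been tested under either reading.

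**Step 4. The other explicit MTD claims below 8 mg.**

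| Scenario | Claimed MTD | Next higher dose: P(overdose) | Agrees with definition? |
|---|---|---|---|
| 25 | 7 mg | 8 mg: 0.193 (printed) | no |
| 26 | 7 mg | 8 mg: 0.387 (re-fit) | yes |
| 30 | 7 mg | 8 mg: 0.422 (re-fit) | yes |
| 31 | 6 mg | 7 mg: 0.363 (printed; re-fit 0.389) | yes |

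Because β > 0, the overdose probability cannot fall as dose rises, so in scenario 31 8 mg fails as well. The re-fits assume 2/6 at 7 mg in scenarios 26 and 30, and 3/6 in scenario 31.

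**Step 5. A second place where the ambiguity matters.** In scenario 29 the table gives 7 mg a target probability of 0.530, above 0.5, while 8 mg has an overdose probability of 0.224, below 0.25. The text makes no MTD claim there. If criterion 1 were applied to 7 mg, the same conflict would arise.

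**The case against.** The strongest reply is that 7.1 first defines the MTD as the highest dose fulfilling EWOC and then words both criteria in terms of the MTD, so the check on higher doses is already built in. That is a fair reading, and it is why a reader should not infer that 7.1 itself contradicts the definition. What stands is that 7.1 does not say so explicitly, and the scenario 25 text does not follow that reading.

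A reader might also cite scenario 14 (1/6 at 4 mg, 1/6 at 6 mg), where 7 mg is still eligible at 0.235. The protocol does not claim 6 mg as MTD there; it lists 7 mg as the next dose.

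A reader might want a rate of occurrence. The documents do not support one. The criteria say the MTD may be considered reached and leave stopping to the SMC, and the rule behind Table 10.2:3 is not given. In illustrative simulations of true curves 1, 3 and 4, stopping at the current dose once a criterion is met with at least 6 patients there gave an MTD below the highest EWOC dose in 19.7%, 13.1% and 23.5% of trials. Requiring that dose also to be the recommended one cut this to 1.9%, 0.8% and 2.3%. Mean sample sizes were 13.1, 13.9 and 13.6 under the first rule and 14.2, 14.6 and 14.9 under the second, against 15.3, 16.8 and 13.6 in Table 10.2:3. Neither rule reproduces the protocol's simulation.

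Finally, the wording is permissive and sits in an illustrative appendix. SAP 7.4.1 will show DLT counts by dose cohort and posterior interval probabilities, so a careful reader could see that 8 mg was untested. That limits the harm but does not make the reported MTD meet its definition.

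**Conclusion.** The conflict is real and rests on the protocol's printed figures. In scenario 25 the text permits 7 mg to be claimed as MTD when 8 mg fulfils EWOC at 0.193 and is the recommended dose. It is one of four explicit MTD claims below 8 mg; the other three agree with the definition. The criteria in 7.1 are ambiguous on the same point, as scenario 29 shows.

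The consequence is that a primary endpoint value could fail its own definition while the tolerability of 8 mg is left undetermined. A reader might go further and say that the objective would be answered negatively. The documents do not support that: nothing in them equates an untested 8 mg dose with an intolerable one.

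The conclusion needs no simulation. It does not depend on the assumed 7 mg data either, since that assumption enters only the re-fits and the patient count for criterion 2. The outcome is permitted, not forced.

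**What to change.** Reconcile the scenario 25 text and the 7.1 criteria with the MTD definition in Protocol 2.1.2 and 7.1 and SAP 5.1. The dose reported as MTD under SAP 7.4.1 should meet that definition on the final data and be kept distinct from an RD, which 3.1 already lets the SMC declare separately. Where a higher provisional dose still fulfils EWOC but was not tested, the report should say so.

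No view is given on which dose should be opened or declared; that stays with the SMC.

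The cost is wording in 7.1 and Appendix 10.2 and a line in SAP 7.4.1. The downside is that some outcomes may be reported as an RD without an MTD.
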